#### 4.4. End of Study Definition

The end of study is considered as the last scheduled study assessment shown in the Schedule of Activities for the last participant in the study. The final data from the study site will be sent to the sponsor (or designee) after completion of the final participant assessment at that study site, in the time frame specified in the Clinical Trial Agreement. The end of the complete study is defined as the timepoint when the last participant completes the last follow-up visit after guselkumab receives regulatory approval for use in pediatric patients or the sponsor discontinues development of guselkumab for the treatment of plaque psoriasis in pediatric patients.

The end of the main study is defined as the timepoint when the last participant completes the Week 52 visit.

### 5. STUDY POPULATION

Screening for eligible participants will be performed within 10 weeks prior to administration of the study intervention. Refer to Section 5.4, Screen Failures for conditions under which the repeat of any screening procedures is allowed.

The inclusion and exclusion criteria for enrolling participants in this study are described below. If there is a question about these criteria, the investigator must consult with the appropriate sponsor representative and resolve any issues before enrolling a participant in the study. Waivers are not allowed.

#### 5.1. Inclusion Criteria

Each potential participant must satisfy all of the following criteria to be enrolled in the study:

1. Participant must be a boy or girl  $\geq 6$  to  $< 18$  years of age.

2. Have a diagnosis of chronic plaque-type psoriasis for at least 6 months (with or without PsA), prior to first administration of study intervention, defined as having at screening and baseline:
  - IGA  $\geq 3$  **and**
  - PASI  $\geq 12$  **and**
  - $\geq 10\%$  BSA involvement **and**at **least one** of the following:
  - very thick lesions **or**
  - clinically relevant facial, genital, or hand/ foot involvement **or**
  - PASI  $\geq 20$  **or**
  - $>20\%$  BSA involvement **or**
  - IGA=4
3. Be a candidate for phototherapy or systemic treatment of plaque psoriasis (either naive or history of previous treatment).
4. Have plaque psoriasis considered by the investigator as inadequately controlled with phototherapy and/or topical therapy after an adequate dose and duration of therapy.
5. Be considered, in the opinion of the investigator, a suitable candidate for etanercept (ENBREL) therapy according to their country's approved ENBREL product labeling.

6. Be otherwise healthy on the basis of physical examination, medical history, and vital signs performed at screening. Any abnormalities, must be consistent with the underlying illness in the study population and this determination must be recorded in the participant's source documents and initialed by the investigator.
7. Contraceptive use by boys or girls should be consistent with local regulations regarding the use of contraceptive methods for those participating in clinical studies.

Before randomization, a girl must be either:

Not of childbearing potential defined as:

premenarchal.

*A premenarchal state is one in which menarche has not yet occurred.*

permanently sterile

*Permanent sterilization methods include hysterectomy, bilateral salpingectomy, bilateral tubal occlusion/ligation procedures, and bilateral oophorectomy.*

or otherwise be incapable of pregnancy.

Of childbearing potential and practicing a highly effective method of contraception (failure rate of <1% per year when used consistently and correctly) and agrees to remain on a highly effective method while receiving study intervention and until 12 weeks after last dose - the end of relevant systemic exposure. Examples of highly effective methods of contraception are in [Appendix 3](#) (Section 10.3); however, the method selected must meet local/regional regulations/guidelines for highly effective contraception

Typical use failure rates may differ from those when used consistently and correctly. Use should be consistent with local regulations regarding the use of contraceptive methods for participants participating in clinical studies.

Note: If the childbearing potential changes after start of the study (eg, a premenarchal girl experiences menarche) or the risk of pregnancy changes (eg, a girl who is not heterosexually active becomes active), a girl must begin a highly effective method of contraception, as described above and in [Appendix 3](#) (Section 10.3).

If reproductive status is questionable, additional evaluation should be considered

8. A girl must agree not to donate eggs (ova, oocytes) for the purposes of assisted reproduction during the study and for a period of at least 12 weeks following the last dose of study intervention.

9. A girl of childbearing potential must have a negative urine pregnancy test at screening and at all visits when study intervention is to be administered.
10. A boy who is sexually active with a female of childbearing potential and who has not had a vasectomy must agree to use a barrier method of birth control (eg, either a condom [with spermicidal foam/gel/film/cream/suppository if available in their locale] or a partner with an occlusive cap [diaphragm or cervical/vault caps] plus spermicidal foam/gel/film/cream/suppository if available in their locale), during the study and for at least 12 weeks after receiving the last administration of study intervention. All boys must also agree to not donate sperm during the study and for at least 12 weeks after receiving the last administration of study intervention.
11. Criterion modified per Amendment 4.
  - 11.1. Are considered eligible according to the following TB screening criteria:
    - Have no history of latent or active TB before screening.
    - Have no signs or symptoms suggestive of active TB upon medical history and/or physical examination.
    - Have had no recent close contact with a person with active TB.
    - Within 10 weeks before the first administration of study intervention, have a negative QuantiFERON®-TB test result ([Appendix 5 \[Section 10.5\]](#)). Within 10 weeks before the first administration of study intervention, a negative tuberculin skin test ([Appendix 5 \[Section 10.5\]](#)) is additionally required if the QuantiFERON-TB test is not approved/registered in that country or the tuberculin skin test is mandated by local health authorities.

Indeterminate or suspected false-positive QuantiFERON®-TB test results should be handled as outlined in [Section 8](#).
12. Must have acceptable evidence of immunity to measles, mumps, rubella, and varicella, which includes any one of the following:
  - a. Documentation of age-appropriate vaccination for measles, mumps, rubella, and varicella that includes both doses of each vaccine (unless local guidelines specify otherwise).

**OR**

  - b. Documentation of past measles, mumps, rubella, and varicella infection by a healthcare provider.

**OR**

  - c. In the absence of (a) or (b) above, must have positive protective antibody titers to measles, mumps, rubella, and varicella prior to the first administration of study intervention.

For participants who have not completed the recommended vaccination schedule for varicella and measles, mumps, and rubella (MMR), and the subsequent vaccination falls within the next 4 years, an accelerated vaccination schedule must be completed prior to

study enrollment if available and required or strongly recommended for the location. If varicella or MMR vaccines are utilized, it is necessary for 2 weeks to elapse between the vaccination and receipt of study intervention.

13. Must agree not to receive a live virus or live bacterial vaccination at least 3 months (or longer as indicated in the package insert of the relevant vaccine) prior to the first administration of study intervention (except for varicella and MMR vaccines), during the study, or within 3 months after the last administration of study intervention.
14. Must agree not to receive a bacille Calmette-Guérin (BCG) vaccination within 12 months of screening, during the study, or within 12 months after the last administration of study intervention.
15. Must avoid prolonged sun exposure and use of tanning booths or other ultraviolet light sources during study.
16. Must have screening laboratory test results within the following parameters:
  - Hemoglobin  $\geq 10$  g/dL (SI:  $\geq 100$  g/L; 6 to 11 years of age)  
 $\geq 12$  g/dL (SI:  $\geq 120$  g/L;  $\geq 12$  years of age)
  - White blood cells  $\geq 3.0 \times 10^3$  cells/ $\mu$ L (SI:  $\geq 3.0 \times 10^9$  cells/L; 6 to 11 years of age)  
 $\geq 4.5 \times 10^3$  cells/ $\mu$ L (SI:  $\geq 4.5 \times 10^9$  cells/L;  $\geq 12$  years of age)
  - Neutrophils  $\geq 1.5 \times 10^3$  cells/ $\mu$ L (SI:  $\geq 1.5 \times 10^9$  cells/L)
  - Platelets  $\geq 150 \times 10^9$ /L
  - Serum creatinine  $\leq 0.7$  mg/dL (SI: 62  $\mu$ mol/L; 6 to 10 years of age)  
 $\leq 1.0$  mg/dL (SI: 88  $\mu$ mol/L; 11 to 12 years of age)  
 $< 1.5$  mg/dL (SI:  $< 133$   $\mu$ mol/L;  $> 12$  years of age)
  - Aspartate aminotransferase (AST)  $\leq 72$  IU/L (6 to 11 years of age)  
 $< 1.5 \times$  ULN for the laboratory conducting the test ( $\geq 12$  years of age)
  - Alanine aminotransferase (ALT)  $\leq 54$  IU/L (6 to  $< 18$  years of age)

If one or more of the above laboratory parameters is out of range, a single retest of laboratory values is permitted.

17. Must be willing and able to adhere to the prohibitions and restrictions specified in this protocol.
18. Must sign an ICF (or their legally acceptable representative must sign) indicating that he or she understands the purpose of, and procedures required for, the study and is willing to

participate in the study. Parent(s) (preferably both if available or as per local requirements) (or their legally acceptable representative) must sign an ICF indicating that he or she understands the purpose of, and procedures required for, the study and is willing to allow the child to participate in the study, as per local requirements. Assent is also required of children capable of understanding the nature of the study (typically 7 years of age and older) as described in Informed Consent Process in [Appendix 2](#) (Section 10.2), Regulatory, Ethical, and Study Oversight Considerations.

## 5.2. Exclusion Criteria

Any potential participant who meets any of the following criteria will be excluded from participating in the study:

### Medical history-related exclusion criteria

1. Currently has nonplaque forms of psoriasis (eg, erythrodermic, guttate, or pustular).
2. Has current drug-induced psoriasis (eg, a new onset of psoriasis or an exacerbation of psoriasis from beta blockers, calcium channel blockers, or lithium).
3. Is pregnant, nursing, or planning a pregnancy or fathering a child while enrolled in the study or within 12 weeks after receiving the last administration of study intervention.
4. Has a history of or current signs or symptoms of severe, progressive, or uncontrolled renal, hepatic, hematological, gastrointestinal, endocrine, pulmonary, cardiac, neurologic, cerebral, or psychiatric disease.
5. Has a transplanted organ (with exception of a corneal transplant > 3 months prior to the first administration of study intervention).
6. Has had major surgery (eg, requiring general anesthesia and hospitalization) within 8 weeks before screening, or will not have fully recovered from such surgery, or has such surgery planned during the time the participant is expected to participate in the study.

Note: Participants with planned surgical procedures to be conducted under local anesthesia may participate.

7. Has unstable suicidal ideation or suicidal behavior:
  - Participants  $\geq 12$  to  $< 18$  years of age may not be randomized if they have:
    - a C-SSRS rating at screening of: suicidal ideation with intention to act (“Ideation level 4”), suicidal ideation with specific plan and intent (“Ideation level 5”), or non-suicidal self-injurious behavior *within the past 6 months, OR*

- a C-SSRS rating at screening of suicidal behavior (actual suicide attempt, interrupted suicide attempt, aborted suicide attempt, or preparatory behaviors for making a suicide attempt) ever (*lifetime*)
  - Participants  $\geq 6$  to  $< 12$  years of age may not be randomized if they have:
    - a C-SSRS rating at screening of: suicidal ideation with intention to act (“Ideation level 4”), suicidal ideation with specific plan and intent (“Ideation level 5”), or suicidal behavior (actual suicide attempt, interrupted suicide attempt, aborted suicide attempt, or preparatory behaviors for making a suicide attempt) or any self-injurious behavior ever (*lifetime*)
  - Participants with a C-SSRS rating at screening of Wish to be Dead (“Ideation level 1”), Non-Specific Active Suicidal Thoughts (“Ideation level 2”), or Active Suicidal Ideation with Any Methods (Not Plan) without Intent to Act (“Ideation level 3”) may not be randomized if:
    - *participants  $\geq 12$  to  $< 18$  years of age* have one of the above C-SSRS ratings *within the past 6 months* and are determined to be at risk by the investigator after being discussed with the medical monitor or designee.
    - *participants  $\geq 6$  to  $< 12$  years of age* have one of the above C-SSRS ratings ever (*lifetime*) and are determined to be at risk by the investigator after being discussed with the medical monitor or designee.
8. Is known to have had a substance abuse (drug or alcohol) problem within the previous 12 months.

#### **Medical therapies-related exclusion criteria**

9. Has previously received guselkumab or etanercept.
10. Has any contraindications to the use of etanercept per local prescribing information.
11. Has received any anti-TNF $\alpha$  biologic therapy (with the exception of etanercept, see exclusion 9) within the previous 3 months before the first administration of study intervention.
12. Is not a suitable candidate for anti-TNF $\alpha$  therapy for the following reasons:
- Has a history of known demyelinating diseases such as multiple sclerosis or optic neuritis.
  - Has known or suspected intolerance or hypersensitivity to anti-TNF $\alpha$  medications (eg, clinical lupus-like syndrome, serum sickness-like reaction).
  - Has a history of, or concurrent congestive heart failure (CHF), including medically controlled CHF.

13. Has received any therapeutic agent directly targeted to IL-12/23, IL-17, or IL-23 within 6 months of the first administration of study intervention (including but not limited to ustekinumab, tildrakizumab, secukinumab, ixekizumab, risankizumab, or brodalumab).
14. Has received natalizumab, efalizumab, or agents that deplete B or T cells (eg, rituximab, alemtuzumab, abatacept, anakinra, or visilizumab) within 12 months of screening, or, if after receiving these agents, evidence is available at screening of persistent depletion of the targeted lymphocyte population.
15. Has received any systemic immunosuppressants (eg, methotrexate [MTX], azathioprine, cyclosporine, 6-thioguanine, mercaptopurine, mycophenolate mofetil, hydroxyurea, and tacrolimus) within 4 weeks of the first administration of study intervention.
16. Has received phototherapy or any systemic medications/treatments that could affect psoriasis or IGA evaluations (including, but not limited to, oral or injectable corticosteroids, retinoids, 1,25-dihydroxy vitamin D3 and analogues, psoralens, sulfasalazine, hydroxyurea, fumaric acid derivatives, herbal treatments, or traditional Taiwanese, Korean, or Chinese medicines) within 4 weeks of the first administration of study intervention.
17. Has used topical medications/treatments that could affect psoriasis or IGA evaluations (including, but not limited to, corticosteroids, anthralin, calcipotriene, topical vitamin D derivatives, retinoids, tazarotene, methoxsalen, trimethylpsoralens, pimecrolimus, tacrolimus, or topical traditional Taiwanese, Korean, or Chinese medicines) within 2 weeks of the first administration of study intervention.
18. Is currently receiving lithium, antimalarials, or intramuscular (IM) gold, or has received lithium, antimalarials, or IM gold within 4 weeks of the first administration of study intervention.
19. Has received an experimental antibody or biologic therapy within the previous 6 months or received any other experimental therapy or new investigational agent (topical or systemic) within 30 days or 5 half-lives (whichever is longer) of any study intervention administration or is currently enrolled in another study using an investigational agent or procedure.
20. Has received, or is expected to receive, any live virus or bacterial vaccination (with the exception of varicella or MMR vaccines; see inclusion criterion 12) within 3 months (or longer as indicated in the package insert of the relevant vaccine) prior to the first administration of study intervention, during the study, or within 12 weeks after the last administration of study intervention.
21. Has had a BCG vaccination within 12 months of screening.

22. Has shown a previous immediate hypersensitivity response, including anaphylaxis, to an immunoglobulin product (eg, plasma derived or recombinant mAb).
23. Has known allergies, hypersensitivity, or intolerance to guselkumab or its excipients (refer to Investigator's Brochure) or etanercept or its excipients.
24. Has known allergy or sensitivity to latex.

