2.5. Definition of Subgroups

To evaluate the consistency of efficacy based on demographic characteristics, baseline disease characteristics, and psoriasis medication history, subgroup analyses will be performed for the co-primary endpoints. The subgroups include, but are not limited to, the following:

Baseline demographics:

- Sex (male, female)
- Race
- Region (North America/Australia/Brazil, Europe)
- Baseline Age (≥ 6 to <12 years, ≥ 12 to <18 years)
- Baseline weight (<70 kg, ≥ 70 kg)

Baseline disease characteristics:

- Age at diagnosis (years) (< 8 , ≥ 8)
- Psoriasis disease duration (years) (< 3 , ≥ 3)
- Baseline PASI (<20 , ≥ 20)
- Baseline IGA (<4 , $=4$)
- Baseline BSA ($<20\%$, $\geq 20\%$)
- Psoriatic arthritis (Yes, No)
- Baseline CDLQI (< 10 , ≥ 10)

Psoriasis medication history:

- Phototherapy (ultraviolet B light [UVB] or psoralen and ultraviolet A light therapy [PUVA])
 - Never used
 - Ever used
- Non-biologic systemics (PUVA, MTX, cyclosporine, acitretin, apremilast, or tofacitinib)
 - Never used
 - Ever Used

- Biologics (infliximab, alefacept, efalizumab, ustekinumab, briakinumab, secukinumab, ixekizumab, brodalumab, or adalimumab)
 - Never used
 - Ever Used
- Non-biologic systemics or biologics (as defined above)
 - Never used
 - Ever used

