4.6. Prior and Concomitant Medications

Subjects' prior psoriasis medication history with topical agents, phototherapy, non-biologic systemic therapies, and biologic medications will be summarized by treatment group for the full analysis set for Part 1 and Part 2 of the study. See Section for lists of medications in each category. In addition, reasons for which subjects discontinued previous systemic therapies (contraindication, inadequate response, intolerance [ie, AEs], or other) will be summarized by treatment group.

The number of subjects who received concomitant treatment with a moisturizer for psoriasis will also be summarized through Week 16 for Part 1.

Subjects who received the following concomitant medications will be listed:

- Corticosteroids (intralesional, IV or oral) for indications other than psoriasis and/or psoriatic arthritis
- Intra-articular corticosteroids

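### SAP 2.5 defines prior biologic and systemic use by closed drug lists, so a child whose only earlier psoriasis drug is unlisted would be classed as never having used one (minor)

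*Protocol*

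**What the plan says.** **Eligibility (protocol 5.1 and 5.2).** Inclusion criterion 3 accepts both treatment-naive and previously treated children. Criterion 9 excludes earlier users of guselkumab or etanercept for life. The other relevant criteria are time-limited washouts:

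- Criterion 11, any anti-TNF biologic other than etanercept: "within the previous 3 months before the first administration of study intervention".
- Criterion 13, agents directed at IL-12/23, IL-17 or IL-23 ("including but not limited to ustekinumab, tildrakizumab, secukinumab, ixekizumab, risankizumab, or brodalumab"): "within 6 months of the first administration of study intervention".
- Criterion 15, systemic immunosuppressants: "eg, methotrexate [MTX], azathioprine, cyclosporine, 6-thioguanine, mercaptopurine, mycophenolate mofetil, hydroxyurea, and tacrolimus) within 4 weeks of the first administration".
- Criterion 16, phototherapy and other systemic treatments that could affect psoriasis, given as an open list: also 4 weeks.

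**Classification (SAP 2.5).** Under psoriasis medication history, the SAP gives an Ever used / Never used split for each class. The biologic class is "Biologics (infliximab, alefacept, efalizumab, ustekinumab, briakinumab, secukinumab, ixekizumab, brodalumab, or adalimumab" and the systemic class is "Non-biologic systemics (PUVA, MTX, cyclosporine, acitretin, apremilast, or tofacitinib". Neither list has an example marker or a residual term. A third split combines the two classes and refers back to these lists as its definition.

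**Use.** Protocol 9.4.1.3 commits to subgroup analyses of the co-primary endpoints by prior medication. SAP 5.2.6 runs them for every subgroup in SAP 2.5, as response proportions by treatment group and differences with exact 95% confidence intervals. SAP 4.6 tabulates prior psoriasis medication by class and says "See Section for lists of medications in each category", with no section number in the text as it reads.

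**The concern.** A closed list is a classification rule. The washouts let in earlier users of drugs that the rule does not recognise, so the rule gives those children the wrong label unless they also used a listed drug. The error has one direction: treated children go into Never used. They also go into Never used of the combined class when nothing listed was taken.

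The subgroup split is there to show whether the response holds in children who have already had systemic or biologic treatment. The protocol (6.5.3) groups tildrakizumab and risankizumab with drugs acting on IL-12, IL-17 or IL-23, and guselkumab itself binds IL-23. Former users of those two agents are therefore among the children a reader would most want to see counted as experienced. If the baseline medication table follows the same lists, it would understate prior treatment as well.

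**Working it through.** No sample size, power or alpha figure in the plan bears on this point, so there is no plan figure to reproduce. The check compares the agents named in the washouts with those named in SAP 2.5.

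| Protocol 5.2 criterion | Washout | Named there | Not in the matching SAP 2.5 list |
|---|---|---|---|
| 11 | 3 months | any anti-TNF biologic except etanercept | any anti-TNF other than infliximab and adalimumab |
| 13 | 6 months | 6 agents | 2: risankizumab, tildrakizumab |
| 15 | 4 weeks | 8 agents | 6: 6-thioguanine, azathioprine, hydroxyurea, mercaptopurine, mycophenolate mofetil, tacrolimus |
| 16 (drug classes, phototherapy set aside) | 4 weeks | 9 classes | 7: systemic corticosteroids, fumaric acid derivatives, herbal treatments, hydroxyurea, sulfasalazine, traditional medicines, vitamin D3 analogues |

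In criterion 16, retinoids are covered only through acitretin and psoralens only through PUVA. Hydroxyurea is in both criteria 15 and 16, so the two together give 6 + 7 − 1 = 12 distinct agents or classes with no place in the systemic list.

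Two passages within the SAP sharpen the contrast. The per-protocol definition (SAP 2.4.1.2) repeats criteria 13, 15 and 16 and names the missing agents. The treatment-failure criteria (SAP 5.1.3.2) end with a residual term that takes in any other systemic or biologic treatment for psoriasis. The history lists have no such term.

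**Size, on assumptions only.** The documents give no prevalence of prior treatment. All percentages below are assumed, apart from results calculated from them.

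1. If 10% to 20% of the 40 guselkumab participants had a prior biologic, the true Ever used cell holds 40 × 0.10 = 4 to 40 × 0.20 = 8.
2. Removing one child from a cell of n changes its response rate by at most 1/n: 1/8 = 12.5 points to 1/4 = 25 points.
3. The same child added to Never used, with 40 − 8 = 32 to 40 − 4 = 36 children, changes that rate by at most 1/33 = 3.0 to 1/37 = 2.7 points.
4. For scale, exact 95% intervals for a single proportion are about 19% to 99% for 3/4 and about 35% to 97% for 6/8. The SAP's planned intervals are for differences; these single-arm ones only show how little such cells can say.
5. If 30% to 50% of the 65 guselkumab and placebo participants had a prior systemic (19.5 to 32.5) and 10% of those had only an unlisted one, about 2 to 3 children are misfiled. If none had only an unlisted drug, the number is 0.

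**The case against.** **The effect is conditional.** A reader might infer that treated children are in fact being analysed as untreated. The documents do not show that. It needs such a child to be enrolled, no listed drug of that class in the child's history, and a literal reading of the list. This stands.

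**On biologics it may be close to hypothetical.** Protocol 2.2 names etanercept, adalimumab and ustekinumab as the biologics approved in paediatric psoriasis in some jurisdictions. The first is excluded for life and the other two are listed. This stands as to likelihood. It does not close the gap, because criteria 11 and 13 still admit former users of other agents, and criterion 19 bars experimental biologics only for 6 months.

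**SAP 2.5 says its subgroups are not limited to those shown.** That sentence governs which subgroups are run, not which drugs belong to a class, so it does not help. Leaving it to the programmer's judgement means that the class is not prespecified.

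**Washout lists and treatment-history lists have different purposes.** Criterion 15 is not confined to psoriasis use, and criterion 16 includes phototherapy and herbal products. A reader might conclude that every agent in those criteria belongs in the SAP lists. That goes too far. It would move phototherapy into the systemic class and count drugs taken for other diseases. This stands and shapes the fix.

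**The link to the SAP 4.6 table is inferred.** The section number is absent, possibly from a broken field or text conversion. SAP 4.6 also covers topical agents, for which SAP 2.5 has no list. SAP 2.5 is the only place with lists for the other classes, so it is the probable target, but it is not confirmed.

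**Conclusion.** The mismatch holds on the text: the SAP's class lists are closed, and the protocol admits earlier users of drugs that they omit. The consequence is a possible misclassification in the prior-medication subgroup summaries of the co-primary endpoints, and probably in the SAP 4.6 table. The number affected is unknown and may be zero. The non-biologic list has the wider gap.

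A reader might take this as a threat to the efficacy conclusion. It is not one. Prior medication is neither a stratification factor (SAP 1.5.1) nor part of the primary comparison (SAP 5.2.3), so the co-primary tests, type I error and power do not change. SAP 5.2.6 plans no subgroup test. At the assumed cell sizes, correct filing would not establish efficacy in experienced children either. Severity is minor. The case for acting is that the rule as written gives a wrong label and is easily corrected.

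**What to change.** In SAP 2.5, replace the two lists by open definitions tied to psoriasis use:

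- *Biologics: any biologic used to treat psoriasis, including but not limited to the agents now listed, tildrakizumab and risankizumab.*
- *Non-biologic systemics: any non-biologic systemic drug used to treat psoriasis, including but not limited to the agents now listed and fumaric acid derivatives.*

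Also:

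- Keep phototherapy in its own class, and settle PUVA, which now sits in both the phototherapy and the systemic class.
- State whether short corticosteroid courses and herbal or traditional products for psoriasis count. Counting them would dilute the experienced group, so the choice should be explicit.
- Assign class from the coded prior-medication data.
- Complete the section reference in SAP 4.6 and say that the table uses the same definitions.

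The cost is one sentence per class and a class-based coding step. SAP 4.6 already requires prior psoriasis medication to be summarised by class, so no new data should be needed. If the Week 16 lock has taken place and the sponsor is unblinded, record the change as a dated clarification and list any child whose class it alters.
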